5.2. Screening Logs

5.2.1. Pre-Screen Log

Participants identified by PI in outpatient clinic who accept a PIS will be included on the pre-screening log. This log will provide the following information:

- Patient initials
- Sequential screening number
- Date of appointment with Gastroenterologist when potential study eligibility determined
- Site (CDDFT or UCLH)
- Eligibility based on clinical history (yes/no)
- Initial screening outcome: recruited, declined, with reason if given
- Telephone discussion with researcher outcome: recruited, declined, with reason if given

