3. STUDY DESIGN

3.1.0verview

A dual-site exploratory, mixed-method feasibility study comprising a serial diagnostic observational study with embedded qualitative design⁷.

[figure not shown]
The sites are:

- County Durham and Darlington NHS Foundation Trust (CDDFT)
- University College London Hospital NHS Foundation Trust (UCLH)

Three elements (high-resolution manometry (HRM), pH/impedance monitoring and qualitative interviews) will be completed in a longitudinal format with 3 overlapping phases, with a recruitment and data collection period of 21 months. Eligible patients will be identified by lead Consultants at CDDFT or UCLH, with initial study participation for those with a new diagnosis within a 3-week period, prior to standard care treatment initiation.

3.2.Study Flow Chart

Sponsor No. 10091 – Protocol - v1.1 – 2022.10.05 IRAS ID: 299013

3.3.Schedule of events

	1) Outpatient appointment	2) Checking eligibility	3) Discussion with potential participant	4) Appointment scheduled at local site	5) Visit 1
What will happen?	 □ Patient identified as potentially eligible □ Patient accepts patient information sheet (PIS) and is willing to be contacted by telephone to discuss the project □ Patient does not accept PIS. Asked if willing to answer question on reason for not wishing to participate. □ If yes, written response obtained 	Pre-screen confirmation of eligibility using medical records	□ Patient contacted a minimum of 48 hours after being given PIS □ Project discussed □ Eligibility discussed □ Patient accepts or declines participation Declines: □ Willing to answer question on reason for not wishing to participate? □ If yes, transcribe this Accepts: □ Appointment date to be scheduled for visit 1	□ Date established with return visit next day □ Pre-test preparation explained: ○ PPI – stop 1 week before ○ Anti-histamine – stop 3 days before ○ Other antacids – stop 24-hours before ○ Fast for 4 hours before tests	□ Written informed consent ○ Physiology ○ Qualitative □ Participant completes 3 questionnaires □ HRM Study as per local SOP □ Start of 24-hour pH/impedance study as per local SOP □ Clinical information relevant to study documented (including endoscopy & biopsy results)
Who?	PI (Consultant Gastroenterologist)	Researcher (CI)	Researcher (CI)	CDDFT: Researcher (CI) UCLH: Administrative Staff or local Clinical Scientist/GI Physiologist	CDDFT: Researcher (CI) UCLH: Clinical Scientist/GI Physiologist

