5.3.1. Informed consent

Eligible participants willing to consider participation will be provided with the study Participant Information Sheet (PIS) by their local PI. If a patient is about to try a new treatment, the PI will explain to the patient that this would commence after the first study visit, to provide baseline measurements. Patients will have a minimum of 48 hours to consider the information before being contacted by the research fellow to discuss the information. This time is kept to a minimum to prevent significant delays to participation and thus treatment initiation. Those wishing to participate will then be provided with an initial appointment date/time. Written informed consent will be obtained at visit 1 by the research fellow or delegated clinical scientist at UCLH, prior to involvement in any part of the study protocol.

A copy of the consent form will be given to the participant, another copy will be stored in the patient's medical records and the original copy will be stored in the site file. The patient's GP will be contacted by letter following the first study visit to inform them that the patient is participating in this research study.

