8. DATA ANALYSIS

8.1. Sample Size

A dual-site recruitment approach will ensure valuable data on recruitment, retention and acceptability are explored, with appreciation of potential differences between secondary care (UHND) and large tertiary referral centres (UCLH). A total of 60 participants will be recruited (30 per site), in keeping with recommendations for feasibility studies¹³. Total eligible EoE cases across sites are approximately 55/year. We envisage at least 60% of patients will consent based on previous experience and PPI input from individuals with EoE, indicating that intended recruitment will be possible over the 21 months. This approach will enable Objectives 1,2 and 3 to be met and ensure a range of symptom profiles are represented (Objective 4), whilst accounting for drop-out (Objectives defined in section 2.2).

A sample size of 20 participants will be recruited to the qualitative interviews. Due to small sample size, information power may not be reached; however, there is evidence to suggest a 20 person cohort would be sufficient to capture the range of perspectives surrounding the acceptability of tests to monitor EoE, with a shared experience of this rare condition forming the focus of the study¹⁴.

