8.2. Outcomes and Analysis

8.2.1. HRM

The following outcomes will be assessed:

- Study recruitment, including practicalities and acceptability of conducting tests prior to treatment initiation (time to test) and site differences. Partial information will be reported, increasing understanding of acceptability.
- Successful completion of test meal during HRM.
- Successful completion of questionnaires for PROMs data.
- Drop-out between initial and post-treatment tests, using information from qualitative interviews to understand barriers.
- Description of changes to diagnostic yield (categorical data) as a result of solid swallows compared to water swallows during HRM, classified in line with routine clinical practice using CCv4.0^{8,15}.
 - This will be described both pre- and post-treatment, providing insight into possible effect size of change in motility classification in EoE (currently unknown) for future study.
 - o Differences will be described in relation to previous treatment exposure and overall symptom status from PROMs.
 - Changes will be described in those recruited with a new diagnosis of EoE versus those recruited as treatment refractory.
- Temporal relationships between patient-reported symptoms and abnormalities identified on HRM will be defined using the oesophageal dysfunction symptom index (D-SI), whereby number of symptoms associated with oesophageal dysfunction is divided by total number of symptoms¹⁶ and numbers in whom typical symptoms are reproduced will be reported.

IRAS ID: 299013

8.2.2. pH/impedance monitoring

The following outcomes will be assessed:

- Recruitment, including practicalities of conducting tests prior to treatment initiation (time to test) and site differences.
- Drop-out between initial and post-treatment tests, using information from qualitative interviews to understand barriers.
- Tolerance of a 24-hour test by patients with EoE.
- Description of mucosal impedance/MNBI as a marker of ongoing inflammation in relation to eosinophilia pre- and post-treatment, with quantitative outcomes described by confidence intervals and treated as preliminary findings.
 - Differences will be described in relation to previous treatment exposure and overall symptom status from PROMs.
- Presence of reflux disease, described using the Lyon Criteria¹².
- Descriptive comparison of histological findings (EoE histologic scoring system/HSS¹⁷) to mucosal impedance results.

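### The pre-screen log starts at acceptance of the information sheet and refusers need not be counted, so a consent rate from it is conditional on acceptance and has a different base from the 60% assumption

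*Protocol*

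**What the plan says.** All references are to the protocol.

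- **Who is logged (5.2.1).** "Participants identified by PI in outpatient clinic who accept a PIS will be included on the pre-screening log". The log has an eligibility field, an initial screening outcome and a telephone outcome. The last reads "Telephone discussion with researcher outcome: recruited, declined, with reason if given", and the initial outcome uses the same two categories.
- **PIS refusers (3.3, step 1).** "Patient does not accept PIS. Asked if willing to answer question on reason for not wishing to participate". A written response is taken only if the patient agrees. Sections 3.6 and 5.1 repeat the optional question for people who decline. None of the three asks for a count.
- **Consent (5.3.1).** "Written informed consent will be obtained at visit 1", which follows the clinic appointment, a wait of at least 48 hours and the telephone call.
- **Participant Identification Log (5.2.2).** This second log holds the date of consent, the sequential screening number and any withdrawal.
- **Planning assumption (8.1).** The supply of patients is given as "Total eligible EoE cases across sites are approximately 55/year". The consent rate applied to that supply is stated next: "We envisage at least 60% of patients will consent based on previous experience and PPI input from individuals with EoE". From these two figures the section concludes that the target of 60 can be met in 21 months.
- **Outcome (8.2.1).** The first item is "Study recruitment, including practicalities and acceptability of conducting tests prior to treatment initiation (time to test) and site differences". Section 8.2.2 also opens with recruitment and site differences.

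**The concern.** The planning rate and the log have different bases. Section 8.1 takes 60% of eligible cases. The log begins one step later, after the patient has accepted the PIS, and sections 5.1 and 5.3.1 offer the PIS only to patients open to taking part. The first point at which a patient can refuse therefore lies outside the record.

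This matters because section 3.7 itself names recruitment as a likely difficulty, given the extra visits and invasive tests. A refusal in clinic is part of the acceptability information the study sets out to collect. The optional free-text answer may give some reasons, but it gives no denominator.

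Site comparison is exposed as well. If the two PIs differ in how they offer the PIS, or their patients differ in how often they refuse it, log-based rates can differ between sites even when consent among eligible patients is the same.

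The log is also inconsistent in itself. Everyone on it has accepted the PIS, and nobody can have consented by the initial screen, yet the initial outcome is either *recruited* or *declined*. Two sites could reasonably complete that field differently.

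**Working it through.** **1. The plan's own figure.** The inputs from 8.1 are 55 eligible cases a year, 21 months and 60% consent.

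- Expected eligible: 55 × 21/12 = 96.25, about 96.
- Expected consents: 96.25 × 0.60 = 57.75, about 58, against a target of 60.
- Rate needed for 60: 60/96.25 = 62.3%, which *at least 60%* allows.

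The target is roughly reproduced, and the base of the 60% is clearly all eligible cases.

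**2. What the log would show.** Let *p* be the consent rate among eligible patients and *a* the share of eligible patients who accept the PIS. The protocol gives no value for *a*, so 0.7 to 1.0 is an assumed range. With dated consents as numerator and logged patients as denominator,

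log-based rate = (*p* × N)/(*a* × N) = *p*/*a*.

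| Assumed *a* | Logged, of 96.25 | Log-based rate if *p* = 60% | *p* if the log shows 60% |
|---|---|---|---|
| 1.0 | 96.25 | 60% | 60% |
| 0.9 | 86.6 | 0.60/0.9 = 66.7% | 0.60 × 0.9 = 54% |
| 0.8 | 77.0 | 0.60/0.8 = 75.0% | 0.60 × 0.8 = 48% |
| 0.7 | 67.4 | 0.60/0.7 = 85.7% | 0.60 × 0.7 = 42% |

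The inflation factor is 1/*a*: 1.11, 1.25 and 1.43 for *a* = 0.9, 0.8 and 0.7.

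**3. Sites.** If both sites had *p* = 60% but *a* was 0.9 at one and 0.7 at the other, the log would show 66.7% and 85.7%. That is a difference of 19 percentage points with no real difference behind it. Both values of *a* are again assumed.

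**4. The numerator.** Section 5.2.2 records the date of consent and the sequential screening number, and section 5.2.1 records the same screening number. Linking the two logs shows who agreed by telephone but never signed. The correct number of consents is therefore available, whatever the pre-screen log calls them.

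**5. What can still be checked.** Dated consents can be set against the 96 or so expected cases: 58 consents is 58/96.25 = 60%, and 60 consents is 62%. This is rough for three reasons:

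- The 55 a year is an approximate planning figure, not an observed count.
- It is not split by site.
- Section 3.1 says the 21 months cover data collection as well as recruitment. If repeat tests took up the last 2 to 4 months, the expected eligible number would be 55 × 19/12 = 87.1 down to 55 × 17/12 = 77.9, and 60 consents would read 68.9% to 77.0%.

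**The case against.** The strongest reply is that the protocol defines no consent rate from this log. It states no recruitment percentage, denominator or progression threshold, and the 60% is a planning figure, not a hypothesis. Section 8.2.1 also promises to report partial information. All of this is right and limits the weight of the point. It does not supply the missing count of refusers.

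It can also be said that an initial outcome of *declined*, kept apart from the telephone outcome, suggests that clinic refusals were meant to be logged. That is possible, but the entry rule in the same section excludes them. The ambiguity is itself a reason to amend the text.

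A reader might infer three stronger things that the documents do not support:

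- *The study's consent rate is overstated.* This holds only for a rate computed from the log, and only if some eligible patients refuse the PIS.
- *The 60% cannot be checked.* The rough comparison with about 96 expected cases remains, and some refusers will leave a written reason.
- *Calling people recruited at the telephone call inflates the rate.* It would do so only if that field were used in place of the date of consent, which section 5.2.2 provides. What remains is a wording problem and one gap: drop-out in 8.2 runs from initial to post-treatment tests, so a loss between the call and Visit 1 is identifiable but belongs to no stated outcome.

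**Conclusion.** The point holds for the denominator. Followed as written, the protocol does not secure a count of the eligible patients approached, and refusals not counted at the time cannot be rebuilt by any later analysis plan. A rate from the log is too high by a factor 1/*a*. For a true 60% that means 67% to 86% over an assumed PIS acceptance of 90% down to 70%, and no error at 100%. The true size is unknown because the protocol gives no acceptance rate.

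The point does not hold for the numerator, which section 5.2.2 secures. The study is descriptive and sets no recruitment threshold, so this does not invalidate it. It is a worthwhile correction to how a leading outcome is recorded, and it should be made early, since each uncounted refusal is lost for good.

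**What to change.** - **Log every patient the PI identifies as potentially eligible.** For PIS refusers, keep one anonymous line: sequence number, site, date, new or known EoE, outcome.
- **Rename the outcomes before consent**, for example: PIS refused, declined by phone, agreed by phone. Define *recruited* as dated written consent.
- **Report consents over all identified eligible patients, by site.** Show the losses at each step, including those between the telephone call and Visit 1.
- **State how eligibility is judged for refusers.** The records check in 5.1 comes after the PIS is accepted, so for refusers it rests on the PI's judgement in clinic.

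The cost is one extra line of PI work per patient and a few log columns. The change does not remove all selection, because the log still depends on whom each PI identifies.

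Separately, section 5.3.1 places written consent, taken at Visit 1, ahead of any study involvement. Sections 3.3 and 5.1 place pre-test preparation, and for new diagnoses a pause in starting treatment, before that visit. These passages must be reconciled. Taking consent remotely after the telephone call would not fully do so, because under 5.3.1 the PI explains in clinic, before the call, that any new treatment waits until after the first visit.

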5.2.2. Participant Identification Log

Participants recruited to the study will be documented within the participation identification log which will include the following information:

- Participant name
- Participant initials
- Sequential screening number
- Participant number

IRAS ID: 299013

- NHS number
- Confirmation of eligibility
- Date of consent
- Personal details (address, phone number, email address)
- Withdrawal (yes/no) if yes, when and why

The researcher will use a checklist to determine clinical eligibility. If recruited, patients will then be assigned a Case Report Form (CRF).

5.3.Consenting Participants

5.3.1. Informed consent

Eligible participants willing to consider participation will be provided with the study Participant Information Sheet (PIS) by their local PI. If a patient is about to try a new treatment, the PI will explain to the patient that this would commence after the first study visit, to provide baseline measurements. Patients will have a minimum of 48 hours to consider the information before being contacted by the research fellow to discuss the information. This time is kept to a minimum to prevent significant delays to participation and thus treatment initiation. Those wishing to participate will then be provided with an initial appointment date/time. Written informed consent will be obtained at visit 1 by the research fellow or delegated clinical scientist at UCLH, prior to involvement in any part of the study protocol.

A copy of the consent form will be given to the participant, another copy will be stored in the patient's medical records and the original copy will be stored in the site file. The patient's GP will be contacted by letter following the first study visit to inform them that the patient is participating in this research study.

5.3.2. Withdrawal of study participants

Participants may withdraw from the study at any point. If this occurs, the primary reason for withdrawal will be documented in the patient's CRF if the participant is willing to provide this information. The individual will be asked whether they wish to:

- i. Withdraw from some aspects of the study but continue in other elements
- ii. Withdraw from all aspects of the study

6. STUDY PROCEDURES

6.1.Covid-19 (Sars-CoV-2)

Local regulations (CDDFT and UCLH) will be adhered to regarding the Covid-19 pandemic.

6.2.Pre-treatment tests

IRAS ID: 299013

6.2.1. Visit 1

PROMs will be collected using three validated questionnaires completed by the patient. These will assess dysphagia, reflux burden and oesophageal hypervigilance and anxiety using the Brief Esophageal Dysphagia Questionnaire/BEDQ¹⁰, Reflux Disease Questionnaire/RDQ¹¹ and Esophageal Hypervigilance and Anxiety Scale/EHAS⁹ respectively.

HRM: HRM involves placement of a nasogastric catheter. Testing will follow standard procedures with additional provocation tests:

- Assessment of 5 mL water swallows
- Rapid drink challenge 200 mL water drunk continuously through a straw. This is used to further assess lower oesophageal sphincter relaxation and oesophageal body pressurisation
- Solid test meal 200g rice eaten to assess oesophageal function using a physiologically relevant test meal

Symptomatic episodes during swallowing will be recorded to determine if reported symptoms correspond with abnormal HRM events, thus assessing the clinical relevance of motility findings. Findings will be classified using the Chicago Classification (CCv4.0)⁸.

pH/impedance monitoring: Following PROMs and HRM, 24-hour ambulatory pH/impedance monitoring using a nasogastric catheter will commence. This involves placement of a second naso-gastric pH/impedance catheter. Testing will follow standard procedures. Patients will be provided with a paper diary to complete and an explanation will be given as to how to use the ambulatory recorder.

6.2.2. Visit 2

Participants will return the ambulatory recorder the following day (24 hours after initiation of ambulatory pH/impedance test).

Individuals will begin treatment course after physiology tests have been performed. Treatment will be standard care (usually locally acting steroids and/or proton pump inhibitors), decided upon by patient and clinician (study does not influence treatment choice). Those patients with an established diagnosis of EoE who are in symptom remission may not begin new treatment course and in this case would only participate in initial tests.

6.3. Qualitative interviews

6.3.1. Visit 3

Qualitative interviews: Semi-structured interviews will be conducted in a sub-set of patients in their preferred medium (telephone/video-conference call/face to face (Sars-CoV-2 permitting)) with support provided. Audio recordings will be made with consent

IRAS ID: 299013

and transcribed verbatim, forming the basis for analysis. Interviews will commence between pre- and post-treatment HRM and pH/impedance tests.

An iterative approach will be taken during the interview process, with data collection and preliminary coding of themes and subthemes to enable the integration and refinement of occurring themes into subsequent interviews.

6.4.Post-treatment tests

6.4.1. Visit 4

HRM: PROMs and HRM will be repeated as described in pre-treatment tests (6.2), two-four months following a course of treatment, to assess physiological changes. Around a similar time, participants will also receive repeat endoscopies with biopsies and clinical assessment as part of standard care.

pH/impedance monitoring: 24-hour ambulatory pH/impedance measurements will be repeated as described in pre-treatment tests (6.2), two-four months following a course of treatment, to assess physiological changes. Again, this will be performed after repeat HRM study. However, should a patient withdraw consent to repeat HRM but wish to repeat the 24-hour ambulatory pH/impedance study, this is acceptable.

6.4.2. Visit 5

Patients will again be required to return the ambulatory recorder 24 hours after the initiation of the pH/impedance test.

7. DATA COLLECTION

7.1. Source Data Documentation

Source data associated with the study is anticipated to include (non-exhaustive list) documents relating to consent, demographics, medical data, adverse events and communications. This will only be accessed by the direct healthcare team. Source data relating to medical information will be recorded within the participant's CRF.

A source data log will be included in the site file to enable easy identification of source data associated with the study. This will include the origin and destination of data, date of data transfer, parties with access to the source data and the type of document. Management of source data will be in line with Good Clinical Practice (GCP) guidance and accordingly, source data will remain accessible to investigators, monitors, auditors and inspectors.

7.2. Case Report Forms

Each participant will have a CRF which will be kept in the site file. This will contain summarised source data relating to an individual's involvement in the study.

IRAS ID: 299013

8. DATA ANALYSIS

8.1. Sample Size

A dual-site recruitment approach will ensure valuable data on recruitment, retention and acceptability are explored, with appreciation of potential differences between secondary care (UHND) and large tertiary referral centres (UCLH). A total of 60 participants will be recruited (30 per site), in keeping with recommendations for feasibility studies¹³. Total eligible EoE cases across sites are approximately 55/year. We envisage at least 60% of patients will consent based on previous experience and PPI input from individuals with EoE, indicating that intended recruitment will be possible over the 21 months. This approach will enable Objectives 1,2 and 3 to be met and ensure a range of symptom profiles are represented (Objective 4), whilst accounting for drop-out (Objectives defined in section 2.2).

A sample size of 20 participants will be recruited to the qualitative interviews. Due to small sample size, information power may not be reached; however, there is evidence to suggest a 20 person cohort would be sufficient to capture the range of perspectives surrounding the acceptability of tests to monitor EoE, with a shared experience of this rare condition forming the focus of the study¹⁴.

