4. STUDY POPULATION

4.1. Number of participants

Recruitment aim of 60 patients (30/site). 20 of these participants will be recruited to semi-structured, qualitative interviews.

4.2.Inclusion criteria

Patients from CDDFT or UCLH with:

- New diagnosis of EoE (>15/high-powered field (hpf) or 0.3mm² on oesophageal biopsy and index oesophageal symptoms).
- Known diagnosis of EoE (current histological and symptom status documented but does not impact inclusion).

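### Section 8.1 uses all 21 months for recruitment, but section 3.1 has the same 21 months include data collection; with Visit 4 inside the period the stated inputs give about 47–54 recruits, not 60

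*Protocol*

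**What the plan says.** Section 8.1 sets the size: "A total of 60 participants will be recruited (30 per site), in keeping with recommendations for feasibility studies". It supports this with an eligible count over both sites and a minimum consent rate: "Total eligible EoE cases across sites are approximately 55/year. We envisage at least 60% of patients will consent". It describes these figures as "indicating that intended recruitment will be possible over the 21 months", and adds that the size allows for drop-out, without giving a rate.

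Section 3.1 describes the same period differently: the three study elements run "with a recruitment and data collection period of 21 months". Section 6.4.1 places the repeat manometry and pH/impedance tests (Visit 4) two to four months after treatment, and section 12.5 ends the study at the last participant's final visit.

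Not everyone has a Visit 4. Under section 6.2.2, patients with established EoE in symptom remission "may not begin new treatment course and in this case would only participate in initial tests". The protocol does not estimate their share.

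**The concern.** One period of 21 months is used in two ways. Section 8.1 counts all of it as recruitment time; section 3.1 has it also contain follow-up. If section 3.1 is right, nobody due Visit 4 can be enrolled in the last two to four months, and the projection in 8.1 is too high.

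Recruitment, site differences and drop-out between initial and repeat tests are listed outcomes in sections 8.2.1 and 8.2.2. If recruitment ran at the stated minimum rate, the study would either appear to miss its target or enrol late participants whose Visit 4 falls outside the period. Objectives 2 and 4 concern treatment response and change, so they depend on participants with both sets of tests. Section 8.1 gives no expected number of those.

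**Working it through.** **Inputs.** Eligible cases: about 55 a year, both sites together (8.1). Consent: at least 60% (8.1). Period: 21 months (8.1, 3.1). Lag to Visit 4: 2–4 months (6.4.1). Target: 60 (8.1). Expected recruits = eligible per year × consent × months/12. At the minimum consent rate this is 55 × 0.60 = 33 a year.

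**1. The plan's own figure, all 21 months used for recruitment**
- 33 × 21/12 = 57.75, about 58 against 60.
- Consent needed for 60: 60 / (55 × 21/12) = 62.3%.
- Eligible cases needed at 60% consent: 60 / (0.60 × 21/12) = 57.1 a year.
- Time needed for 60: 60 / 33 × 12 = 21.8 months.

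**2. Visit 4 inside the 21 months, everyone due Visit 4**

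| Lag | Enrolment window | Expected recruits | Short of 60 | Consent needed for 60 |
|---|---|---|---|---|
| 2 months | 19 months | 33 × 19/12 = 52.25 | 7.75 (13%) | 60 / (55 × 19/12) = 68.9% |
| 4 months | 17 months | 33 × 17/12 = 46.75 | 13.25 (22%) | 60 / (55 × 17/12) = 77.0% |

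At 60% consent, the total duration for 60 recruits with follow-up is 21.8 + 2 = 23.8 to 21.8 + 4 = 25.8 months.

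**3. Allowing for single-visit participants.** Let a share s of consenting patients have initial tests only, so that they can be enrolled to month 21. The protocol gives no value for s; I assume 10–40%. Expected recruits = s × 57.75 + (1 − s) × (46.75 or 52.25).
- s = 10%: 5.775 + 42.075 = 47.9 (4-month lag); 5.775 + 47.025 = 52.8 (2-month lag).
- s = 40%: 23.1 + 28.05 = 51.2 (4-month lag); 23.1 + 31.35 = 54.5 (2-month lag).

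The range is about 48–54. Single-visit participants raise the number recruited but add no before-and-after data.

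**4. Paired data, illustration only.** Under the same assumed s, those due Visit 4 number between 28.05 (s = 40%, 4-month lag) and 47.0 (s = 10%, 2-month lag). With an assumed drop-out of 10–30%, pairs run from 28.05 × 0.70 = 19.6 to 47.0 × 0.90 = 42.3. The width of that range shows why the protocol needs to state its own assumptions.

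**The case against.** The strongest reply is that 8.1 offers approximate inputs and a floor. Over a full 21 months, 62.3% consent or about 57 eligible cases a year gives 60, and both fit the wording. This stands: a reader might infer that 8.1 contains a multiplication error or that 60 is out of reach, and the protocol supports neither. The same allowance does not easily cover the timeline gap. For example, 70% consent at 55 a year gives 55 × 0.70 × 19/12 = 61.0 over 19 months, but 54.5 over 17.

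A second reply is that the 47–52 range binds only participants due Visit 4. This also stands, which is why the mixed calculation is shown; at 60% consent it still falls below 60. Nor does the protocol say whether the 55 a year includes patients with an existing diagnosis. If they come on top of it, recruitment could be higher.

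Third, 60 is the number recruited, partial data will be reported, and the drop-out phrase can mean that 60 already includes those who will leave. That is a fair reading, but it leaves the expected number with repeat tests unstated.

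Finally, a reader might conclude that the target of 30 per site is wrong. At 60% consent over 21 months it needs 30 / (0.60 × 21/12) = 28.6 eligible cases a year at each site, but the 55 is not split by site, so the target cannot be checked either way.

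**Conclusion.** Sections 8.1 and 3.1 conflict over what the 21 months contain, and the recruitment claim in 8.1 depends on which is meant. If all 21 months are recruitment, the stated inputs give about 58: consistent with 60, with no visible margin for drop-out. If Visit 4 must fall inside the period, as section 3.1 indicates, they give about 47–52 with everyone due Visit 4, or about 48–54 under an assumed 10–40% single-visit share.

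These figures rest on even accrual, 55 cases a year, exactly 60% consent and a lag of 2–4 months from enrolment. Up to three weeks before first tests for new diagnoses (section 5.1), or counting the lag from the end of a treatment course, would shorten the window further.

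The study tests no hypothesis and attaches no success threshold to 60, so no power claim is affected. What needs correcting is a stated size that the design's own minimum inputs do not deliver within its stated period. The paired-data range is illustrative and should not be read as showing that any stated paired number is wrong; the protocol states none.

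**What to change.** In sections 3.1 and 8.1, state the recruitment window and the follow-up period separately. Then do one of the following, and carry the result into sections 3.6 and 4.1:

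- keep a 21-month total and restate expected recruitment at 60% consent as about 47–54, saying what share is assumed to be single-visit; or
- keep 60 and state what it requires: about 69–77% consent if all are due Visit 4, or about 24–26 months in total at 60%.

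In 8.1, also give the assumed drop-out rate, and the expected number with both Visit 1 and Visit 4 data separately from the number recruited. Saying whether the 55 a year includes known diagnoses, and how it divides between sites, would let a reader check the 30-per-site target; changing that target is not required.

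The first option costs only wording and needs no extra patients, but the stated figure becomes less favourable. Keeping 60 at 60% consent costs about 3–5 months of extra study time (23.8 − 21 = 2.8 to 25.8 − 21 = 4.8).
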